### 8.3.3 MBA-9

The MBA-9 scale is completed by the investigator and addresses core symptoms of RTT. MBA-9 was derived from the full MBA scale (37 RTT symptoms) by selecting the items that are deemed to be amenable to change and that reflect areas of meaningful clinical change. The severity of current symptoms is rated on a 5-point numerical scale; 0 = normal or never; 1 = mild or rare; 2 = moderate or occasional; 3 = marked or frequent; 4 = very severe or constant. The MBA-9 score is calculated by summing the scores of the individual items. The maximum score is 36 and higher scores represent greater severity.

MBA-9 scores and their change from baseline will be summarized by treatment and visit.

### 8.3.4 Children's Sleep Habit Questionnaire

The CSHQ includes a total sleep disturbance score and 8 sleep subscales: bedtime resistance, sleep onset delay, sleep duration, sleep anxiety, night wakings, parasomnias, sleep disordered breathing and daytime sleepiness. The items included in each subscale are presented in [Table 5](#).

**Table 5 CHSQ Subscales**

Subscale	Items Included
Bedtime resistance	1*, 3*, 4, 5, 6, 8
Sleep onset delay	2*
Sleep duration	9, 10*, 11*
Sleep anxiety	5, 7, 8, 21
Night wakings	16, 24, 25
Parasomnias	12, 13, 14, 15, 17, 22, 23
Sleep disordered breathing	18, 19, 20
Daytime sleepiness	26*, 27, 28, 29, 30, 31, 32, 33

\* These items are to be reverse scored.

The responses to each item of the CSHQ are to be scored as Usually=3, Sometimes=2, Rarely=1, except for the items marked with \* in Table 5, which are considered to be “desirable” sleep behaviors and are therefore reverse scored. Items 32 and 33 are scored 1 for “not sleepy”, 2 for “very sleepy”, 3 for “falls asleep”.

CSHQ scores and CSHQ subscale scores along with their change from baseline will be summarized by treatment and visit.

### 8.4 Exploratory Efficacy Endpoints

The analysis of exploratory efficacy endpoints will be descriptive, using summaries by treatment arms.

#### 8.4.1 Caregiver Quality of Life Questionnaire

The caregiver's health-related quality of life will be assessed using the 36-item short form (SF-36). The SF-36 measures 8 domains of health-related quality of life: 1) limitations in physical activities because of health problems; 2) limitations in social activities because of physical or emotional problems; 3) limitations in usual role activities because of physical health problems; 4) bodily pain; 5) general mental health (psychosocial distress and well-being); 6) limitations in usual role activities because of emotional problems; 7) vitality (energy and fatigue); and 8) general health perceptions. These domains are used to calculate 2 composite scores, the physical health composite score (PCS) and the mental health composite score (MCS).

The items included in each subscale are presented in [Table 6](#).

**Table 6 SF-36 Subscales**

Subscale	Items Included
Physical functioning	3 (a to j)
Role-physical	4 (a to d)
Bodily pain	7 and 8
General health	1 and 11 (a to d)
Vitality	9 (a, e, g and i)
Social functioning	6 and 10
Role-emotional	5 (a to c)
Mental health	9 (b, c, d, f and h)

The raw SF-36 data will be sent to Optum via Rave Web Services so that the subscales and composite scales can be scored by the QualityMetric Health Outcomes™ Scoring Software 5.0. The scores will then be uploaded into the electronic database.

The scoring of the SF-36 questionnaire via the QualityMetric Health Outcomes™ Scoring Software 5.0 is based on norm-based scoring which ensures that the scores for the subscales have a mean of 50 and a standard deviation of 10, based on the 2009 US general population (Maruish, 2011). A higher score is indicative of a better health state.

The steps that the software follows to score the scales and composite scales are summarized below:

1. Some of the items are recoded to ensure that a higher score corresponds to a better health state for all items in the SF-36.
2. The raw scores for the health domain scales are calculated as the sum of the final response values for the items included in each scale.
3. Transform the score to a 0-100 scale score:

Transformed scale score = (Actual raw score - Lowest possible raw score)/Possible raw score range x 100

4. Transform to z-scores ~ Normal(0,1) according to the 2009 US general population norms.
5. Calculate T scores for each domain =  $T \text{ score} = 50 + (\text{domain } z\text{-score} \times 10)$ . T scores calculated to aid interpretation.
6. Finally calculate MCS and PCS using a 3 step procedure:

First, the eight health domain scales are standardized using means and standard deviations

from the 2009 U.S. general population. Second, these standardized scores are aggregated using weights (factor score coefficients) from the 1990 U.S. general population. Third, aggregate PCS and MCS scores are standardized using a linear *T*score transformation with a mean of 50 and a standard deviation of 10.

SF-36 composite scores and SF-36 subscale scores along with their change from baseline will be summarized by treatment and visit.

#### 8.4.2 Patient Quality of Life Questionnaire

This instrument is a well-validated general QoL measure in pediatric populations with chronic illness. It measures QoL of the child and the family by parent or child report. The caregiver will be asked to complete the questionnaire on behalf of the patient. The CHQ-PF50 covers multidimensional health concepts including Physical Functioning, Role/Social Limitations–Emotional/Behavioral, Role/Social Limitations– Physical, Behavior, Mental Health, Self-Esteem, General Health , Bodily Pain, Family Activities, Parent Impact–Time, Parent Impact–Emotional, and Family Cohesion. Scores for specific items and subscales, as well as a standardized physical summary (PhS) score and a standardized psychosocial summary (PsS) score, can be calculated from the CHQ-PF50 questionnaire. Scores are based on a 0 to 100 scale and higher scores indicate better quality of life.

Table 7 presents the items included in each health concept.

**Table 7 CHQ-PF50 Health Concepts**

Health Concept	Items Included
Global health item	1.1
Physical functioning	2.1 (a to f)
Role/social limitations due to emotional/behavioral difficulties	3.1 (a to c)
Role/social limitations due to physical health	3.2 (a to b)
Bodily pain and discomfort	4.1 and 4.2
Behavior	5.1 (a to e) and 5.2
Global behavior item	5.2
Mental health	6.1 (a to e)
Self esteem	7.1 (a to f)
General health perceptions	8.1 (a to e) and 1.1
Change in health item	8.2
Emotional impact on parent	9.1 (a to c)
Time impact on parent	9.2 (a to c)
Family activities	9.3 (a to f)
Family cohesion item	9.4

Details regarding the scoring of the health concepts of CHQ-PF50 and of the PhS and PsS can be found in [Appendix 5](#). All of the health concepts and scales included in CHQ-PF50, except for the change in health item are continuous.

CHQ-PF50 standardized scores (as per Appendix 5) CHQ-PF50 subscale scores, PhS and PsS scores along with their change from baseline will be summarized by treatment and visit.

### **8.4.3 Hospital Services Use Questionnaire**

The Hospital Services Use Questionnaire captures the frequency of hospital visits and patient hospitalizations. The responses to this questionnaire will be summarized by treatment group for the baseline and treatment periods.

### **8.4.4 Caregiver Assessment of Rett Symptoms**

The Caregiver Assessment of Rett Symptoms is a symptom diary, including 12 items, each scored between 0 and 10, where a higher score for all items except items 1 and 9 represents a greater severity. Items 1 and 9 will be reverse-scored and a total score will be calculated as the sum of items 1 to 10, 11a and 12a. For items 11 and 12, if 11 is 'No' then 11a should be scored 10 and if 12 is 'No' then 12a should be scored 0. A visit score will be derived for each item and for the total score as the mean of the scores since the previous visit.

The total scores and the scores for each item of the Caregiver Assessment of Rett Symptoms along with change from baseline will be summarized by visit and treatment group.

## **9. Safety and Tolerability Analysis**

### **9.1 Adverse Events**

All reported AEs will be classified by system organ class (SOC), preferred term and lower level term using Version 21.1 of MedDRA or higher.

Summaries will be presented by treatment group as well as SOC and preferred term.

The following summaries will be generated (counts are by patient unless specified otherwise):

Overall summary of AEs, including number of patients reporting each of; Treatment Emergent Adverse Events (TEAEs), TEAEs that started during the titration period as applicable, treatment-related TEAEs, treatment-related TEAEs that started during the titration period, TEAEs leading to withdrawal, treatment-related TEAEs leading to withdrawal, serious TEAEs, treatment-related serious TEAEs.

- Summary of TEAEs.
- Summary of TEAEs by event (PT).
- Summary of treatment-related TEAEs.
- Summary of treatment-related TEAEs by event
- Summary of TEAEs by maximal severity.
- Summary of TEAEs by sex.
- Summary of serious TEAEs.
- Summary of serious TEAEs by event.
- Summary of non-serious TEAEs.
- Summary of non-serious TEAEs by event (PT).
- Summary of treatment-related serious TEAEs.
- Summary of treatment-related serious TEAEs by event (PT).
- Summary of TEAEs leading to permanent discontinuation of IMP.
- Summary of treatment-related TEAEs leading to permanent discontinuation of IMP.

- Summary of TEAEs leading to IMP dose reduction excluding permanent discontinuation (by resolution and overall).
- Summary of treatment-related TEAEs leading to IMP dose reduction excluding permanent discontinuation (by resolution and overall).
- Summary of TEAEs leading to temporary IMP dose reduction (by resolution and overall).
- Summary of treatment-related TEAEs leading to temporary IMP dose reduction (by resolution and overall).
- Summary of TEAEs leading to permanent IMP dose reduction excluding permanent discontinuation (by resolution and overall).
- Summary of treatment-related TEAEs leading to permanent IMP dose reduction excluding permanent discontinuation (by resolution and overall).
- Summary of fatal TEAEs.
- Summary of TEAEs by time of first onset of AE.
- Summary of TEAEs by time to AE resolution.
- Summary of TEAEs reported in  $\geq 2\%$  of patients (after rounding) in the GWP42003-P treatment groups and where the incidence is greater than the (pooled) placebo treatment group.
- List of patients experiencing TEAEs by SOC and preferred term.
- Summary of pre-treatment AEs.

For the summary of TEAEs by maximal severity, for each patient, the worst severity recorded by preferred term, SOC and overall will be used for summary purposes. If severity is missing, the worst case (severe) will be assumed.

For summaries by resolution, AEs with an outcome of 'recovered' or 'recovered with sequelae' will be summarized as 'Resolved' and AEs with an outcome of 'continuing', 'patient died' or those with a missing outcome will be summarized as 'Continuing'. For each patient, preferred term and SOC, if both 'Resolved' and 'Continuing' AE are present in database, only the 'Continuing' one will be presented in outputs.

For the summary of TEAEs by time of first onset of AE, data will be summarized under the following categories:

- Week 1 (Day 1–7).
- Week 2 (Day 8–14).
- Weeks 3–6 (Day 15–42).
- Weeks 7–10 (Day 43–70).
- Weeks 11–14 (Day 71–98).
- Weeks 15–18 (Day 99–126).
- Weeks 19–22 (Day 127–154).
- $>22$  weeks ( $>$  Day 154).

If patients have multiple occurrences of an AE then the AE will be counted once for the first occurrence only. Percentages will be based on the number of patients in the safety analysis set who have a visit or follow-up call within each time period above. In case there is no planned visits in the interval, percentages will be based on the number of patients in the safety analysis set.

For the summary of TEAEs by time to AE resolution, data will be summarized under the following categories:

- 1 week ( $\leq 7$  days).
- 2 weeks (8–14 days).
- 3 weeks (15–21 days).
- 4 weeks (22–28 days).
- $>4$  weeks ( $>28$  days).
- Ongoing (for AEs not resolved).

If patients have multiple occurrences of an AE then the AE will be counted once for the occurrence with the longest time to AE resolution. However, if any of the AEs are not resolved then the AE will be counted once within the ‘Ongoing’ category.

The start and stop day of the AE relative to the first dose of IMP (as recorded on the eCRF) will be calculated as per [Section 6.1.56.1.5](#). For partial dates, if it is clear from the partial date that the start/stop day was prior to the first dose of IMP, then ‘pre’ will be listed, similarly if it is clear that the event was post the first dose of IMP then ‘post’ will be listed as the start/stop day as appropriate. If it is not clear whether it is pre or post first dose of IMP, then day is not calculated, field is left blank.

All AEs will be listed. Listings will include the start and stop day of the AE, a flag for treatment emergence, and limited demographic information about the patient (age, sex, race and weight at screening). A separate listing will be provided for pre-treatment AEs, serious AEs and events of special interest (see [APPENDIX Appendix 2](#)).

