12.6 Reporting Procedures for All Adverse Events

All AEs (including SAEs) occurring during the trial will be reported on the running logs in the AE section of the eCRF. This includes all events from the time following screening (Visit 1) up to and including the post-trial follow-up visit (Visit 11), whether or not attributed to IMP and observed by the investigator or patient.

For the patient's expected seizure types, these do not routinely require documentation as AEs. However, any worsening, including change in the pattern or severity of seizures should be documented in the eCRF if deemed to meet the definition of an AE, in the investigator's opinion.

Any AE which meets SAE criteria should still be reported as a SAE.

The following information will need to be provided for all AEs:

A) Adverse Event (Diagnosis or Syndrome if Known, or Signs and Symptoms)

Where the investigator cannot determine a diagnosis, signs or symptoms should be recorded in the AE section of the eCRF. Once a diagnosis has been determined the AE section of eCRF must be updated to reflect the diagnosis in replacement of the original symptoms. In circumstances where only a provisional diagnosis is possible (working diagnosis), the eCRF must be updated to reflect the provisional diagnosis in replacement of the original symptoms. In some circumstances it may be relevant for the investigator to include the symptoms alongside the diagnosis in the verbatim event description.

Study Code: GWND18064

EudraCT Number: 2018-003370-27

Clinical Protocol 4.1, 07Jul2020 (duplicate synopsis removed)

However, the diagnosis (full or provisional) should be clearly stated, e.g., fever and malaise due to respiratory tract infection.

B) Adverse Event Start Date and Stop Date

The start and stop dates of the event must be provided. All AEs require these fields to be completed in full. Partial dates or missing dates are not normally acceptable and significant effort must be undertaken to obtain any unknown information. If a precise date is not known an estimated date should be provided instead. When a complete date cannot be given, record as much information as possible (i.e., month and year or, in exceptional circumstances, just year). When the actual start date becomes known the eCRF must be updated to replace the previously recorded date.

C) Outcome

The outcome of the event must be recorded accurately and classified into 1 of the following categories:

- Recovered.
- Recovered with sequelae.

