#### **6.1.9.1 Adverse events**

A TEAE is defined as an AE with a start date on or after the first dose of IMP. If an AE has a partial start date and it is unclear from the partial date (or the stop date) whether the AE started prior to or post first dose of IMP then the AE will be considered treatment emergent. If the start date of the AE is the same as the date of first dose of IMP then the AE will be considered treatment emergent.

A TEAE will be considered treatment-related if the plausibility relationship to IMP is recorded on the eCRF as ‘yes’. If the data on plausibility relationship to IMP is missing then the TEAE will be considered treatment-related.

A TEAE will be considered leading to permanent discontinuation of IMP (leading to withdrawal) if the action taken with IMP is recorded on the eCRF as ‘trial medication stopped’ or the outcome is recorded on the eCRF as ‘patient died’.

A treatment-related TEAEs leading to withdrawal is a TEAE leading to permanent IMP

discontinuation and considered treatment-related as per above definition.

A TEAE will be considered leading to IMP temporary discontinuation if the action taken with IMP is recorded on the eCRF as 'trial medication interrupted'.

A TEAE will be considered leading to permanent IMP dose reduction excluding permanent discontinuation if the action taken with IMP is recorded on the eCRF as 'dose reduced'.

An AE will be considered fatal if the outcome is recorded on the eCRF as 'patient died'.

The time to first onset of AE will be calculated for TEAEs as:

Start date of AE – Date of first dose of IMP + 1

The time to AE resolution will be calculated for TEAEs as:

Stop date of AE – Start date of AE + 1

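### SAP 9.1 classes fatal adverse events as 'Continuing' in the by-resolution dose-reduction summaries, and the time-to-resolution table gives them no correct row

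*SAP*

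**What the plan says.** SAP 9.1 sets two classes for summaries by resolution. The first is "AEs with an outcome of 'recovered' or 'recovered with sequelae' will be summarized as 'Resolved". The second takes everything else: "patient died' or those with a missing outcome will be summarized as 'Continuing". If a patient has both classes under one preferred term and system organ class, only the 'Continuing' record is shown.

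The tables that carry the by-resolution label in the SAP 9.1 list are the six dose-reduction summaries, for example "Summary of TEAEs leading to temporary IMP dose reduction (by resolution and overall".

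The same list contains a further table, "Summary of TEAEs by time to AE resolution". SAP 6.1.9.1 gives its derivation: "The time to AE resolution will be calculated for TEAEs as" followed by "Stop date of AE – Start date of AE + 1". SAP 9.1 then gives this table five duration rows and an 'Ongoing' row for events that are not resolved. Any unresolved occurrence moves the term to that last row.

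SAP 6.1.9.1 also treats a fatal treatment-emergent event as leading to permanent discontinuation whatever action was recorded: "or the outcome is recorded on the eCRF as ‘patient died".

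Protocol 12.6 lists four outcomes: recovered, recovered with sequelae, continuing, and patient died. Of the start and stop dates it says "All AEs require these fields to be completed in full".

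**The concern.** A fatal event is neither continuing nor resolved. The eCRF collects death as its own outcome, and the SAP merges it with two different things: an event still in progress and an outcome nobody recorded. In a by-resolution table, the reader could not tell a death from an unfinished mild event of the same term.

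The time-to-resolution table has a related gap. Its formula needs only a start and a stop date. If sites close a fatal event with a stop date, the formula returns a number of days, and nothing in SAP 6.1.9.1 stops that number from being used. Whether it is used depends on what 'not resolved' means in SAP 9.1, and that is not defined for this table.

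At stake is the labelling of the gravest outcome in tables meant to show how events ended. The SAP has dropped inferential analysis, so these tables are part of the reported result.

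**Working it through.** The documents state no figure on this point, so there is none to reproduce. The check is to follow a fatal event through each rule.

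**1. By-resolution tables.** There are three pairs, each with an all-causality and a treatment-related version.

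| Pair | Title excludes permanent discontinuation? | Can a fatal event enter? |
|---|---|---|
| Dose reduction | Yes | Not by title; SAP 6.1.9.1 counts every fatal event as permanent discontinuation |
| Temporary dose reduction | No | Yes, if the recorded action qualifies |
| Permanent dose reduction | Yes | Not by title, but see below |

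So 2 + 2 = 4 tables exclude fatal events by title, and 6 − 4 = 2 do not. The exclusion is not watertight: SAP 6.1.9.1 defines the permanent dose-reduction category by the action 'dose reduced' alone, without an outcome condition. A fatal event recorded with that action meets both definitions. In every case the event enters only if its action was a dose reduction or interruption. Once in, it is labelled 'Continuing'.

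**2. Time-to-resolution table.** Two readings are possible.

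- *Outcome reading.* 'Not resolved' follows the class definition given earlier in SAP 9.1. Only the two recovered outcomes count as resolved, so a fatal event goes to 'Ongoing' whatever its dates.
- *Date reading.* The formula is applied to any event with a stop date.

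The documents give no fatal event, so the dates here are assumed: start on Day 50, stop date equal to the date of death.

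| Death on | Stop − start + 1 | Date reading | Outcome reading |
|---|---|---|---|
| Day 53 | 53 − 50 + 1 = 4 days | 1 week | Ongoing |
| Day 57 | 57 − 50 + 1 = 8 days | 2 weeks | Ongoing |
| Day 70 | 70 − 50 + 1 = 21 days | 3 weeks | Ongoing |
| Day 90 | 90 − 50 + 1 = 41 days | >4 weeks | Ongoing |

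**3. Missing stop dates.** SAP 6.1.7.1.3 imputes missing or partial stop dates unless the event is ongoing, and uses the result for time to resolution. Fatal events are not mentioned. Under the date reading, the interval for a fatal event could therefore be partly imputed.

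**4. Where deaths are otherwise shown.** SAP 9.1 plans summaries of fatal events, serious events and events leading to permanent discontinuation. SAP 6.1.9.1 sends every fatal treatment-emergent event to the last of these. All adverse events are listed, and serious ones are listed separately.

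**The case against.** A reader might infer that the SAP contradicts itself, showing a death as ongoing in one set of tables and as quickly resolved in another, and that this flatters the safety profile. The documents do not support that. SAP 9.1 defines 'Resolved' by outcome, and its time-to-resolution table has a row for unresolved events with an override that favours that row. Read together, they put a fatal event in 'Ongoing', which agrees with 'Continuing' in the by-resolution tables. The contradiction and the favourable direction arise only under the date reading, which the SAP leaves open but does not state.

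A reader might also take it that all six dose-reduction tables are affected. Four are titled to exclude the category into which the SAP puts every fatal event, and the other two need a particular recorded action. Few fatal events, perhaps none, would get there.

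The stop-date premise is partly inference. Protocol 12.6 asks for both dates but also allows the outcome 'continuing', so a stop date cannot be universal. Neither document says that a fatal event is closed on the date of death.

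Finally, grouping deaths with unresolved events is the unfavourable direction, and the words 'not resolved' do describe a death. This is fair for the direction of any error. It does not rescue the labels: 'Continuing' and 'Ongoing' are still wrong for an event that ended in death. The by-resolution rule names death explicitly, so it is a stated misclassification and not merely a missing detail.

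**Conclusion.** The point holds in a limited form. SAP 9.1 expressly labels fatal events 'Continuing' in the by-resolution summaries. The time-to-resolution table offers a fatal event only 'Ongoing', on the more natural reading, or a resolved interval, on the date reading. No available label is correct.

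The effect is small. It is confined to descriptive safety tables; no endpoint or analysis population depends on it. Deaths remain visible in three other summaries and in the listings. The number of deaths is not given, and neither are the numbers analysed per arm in a trial that the sponsor discontinued, so a percentage would rest on invented inputs and none is offered. The date reading further assumes that fatal events carry a stop date. Priority: minor.

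**What to change.** In SAP 9.1, use three classes for summaries by resolution:

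- 'Resolved': recovered, or recovered with sequelae.
- 'Continuing': continuing, or outcome missing.
- 'Fatal': patient died.

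Within a patient and term, let 'Fatal' take precedence over 'Continuing', and 'Continuing' over 'Resolved'. A fatal event that reaches a dose-reduction table through its action field would then at least be labelled as what it is.

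In SAP 6.1.9.1, calculate time to resolution only for the two recovered outcomes. This also removes the question of imputed stop dates for fatal events in that table. In SAP 9.1, add a 'Fatal' row to the time-to-resolution table with the same precedence.

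The cost is a few sentences in the SAP, the matching change to the table shells, and minor programming. The outcome is already collected on the eCRF, so no new data are needed.
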